In the first year of presentation, approximately 1 in 10 survivors and close contacts presented with cataract (unpublished data). Such cataracts may be due directly to either intraocular inflammation or long-term steroid use, often needed to address the severe panuveitis present in disease, but may

also develop naturally. Cataract surgery is cost-effective and clearly indicated to help vision, but without knowledge of whether viral persistence exists, it is not known what infection control practices are necessary for surgery to be performed safely.

A similar proportion of patients have developed post-inflammatory epiretinal membrane (which requires more complex vitreoretinal surgery to address). Therefore, a need exists for the long-term development of surgical capacity in addition to short-term knowledge regarding intraocular persistence of virus. Although the mainstay of EVD treatment is largely medical, it is clear that a significant proportion of ophthalmic sequelae will require surgical intervention.

For survivors who are blind, cataract surgery is necessary to restore visual function, allowing re-integration into society, and for personal safety, to avoid falls and collisions. However, surgical outcomes among Ebola survivors are unknown. Ebola-associated ocular comorbidities such as hypotony must be accounted for post surgically. Given that cataracts associated with the rubella virus are characterized by severe postoperative inflammation due to viral persistence within the lens, requiring aggressive postoperative anti-inflammatory treatment with steroids, we must monitor intraocular inflammation in the postoperative period. Intraocular surgery among young individuals is also often marked by a robust inflammatory response. Both factors may influence outcomes in Ebola-associated cataract. We propose the study of surgical outcomes that will inform care in other affected countries and for future Ebola-affected patients.

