#### 3.0 PARTICIPANTS

This study involves recruiting EVD survivors and controls who have a clinical need for cataract surgery, which will be performed using the small incision cataract surgery technique which is standard practice in Liberia. Therefore, we will enroll all individuals who meet study eligibility criteria and would otherwise be eligible (clinically) to undergo cataract surgery.

The accrual ceiling is 120 people, with up to 60 EVD survivors and up to 60 controls. Current estimates of numbers of survivors and controls meeting eligibility criteria is lower, at about 35-45 survivors and 35 controls.

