# 3.1 Participant Eligibility Criteria

## 3.1.1 Inclusion Criteria

To be eligible, the following inclusion criteria must be met, where applicable.

- 1. Participant must be 14 years of age or older.
- 2. Participant must be able to understand and sign an informed consent or have a parent/legal guardian do so if they are minor children or a legally authorized representative to provide consent for adults without consent capacity.
- 3. Participant must be either:
  - a. an Ebola virus disease (EVD) seropositive survivor or seropositive control OR
  - b. an EVD seronegative survivor or seronegative control (Serology confirmation is available for PREVAIL participants and will be conducted for non-PREVAIL participants.).
- 4. Participant must have visually significant cataract(s) consistent with level of visual deficit.
- 5. Participant must have corrected visual acuity worse than 20/40 in affected eye and vision loss believed to be primarily the result of the cataract.
- 6. Any women and persons of childbearing age must have a negative pregnancy test at screening and must be willing to undergo pregnancy testing prior to the cataract surgery.

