# 9.0 STATISTICAL ANALYSIS

This protocol has sample sizes of convenience, in that all identified Ebola survivors who are eligible for surgery and all controls in the PREVAIL III protocol will be invited to participate, in addition to some Ebola survivors from an outlying region. Therefore, statistical analysis will be limited to what can be derived using those resultant sample sizes. Controls who are seropositive will be analyzed separately and will not serve as "controls" for statistical calculations. Similarly, seronegative survivors will not be treated as survivors in the primary analyses.

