# 9.1 Analysis of Data / Study Outcomes

If all PCR results and/or immunohistochemistry results are negative, simple models which assume independence across eyes from the same individual will be used to construct a 95% confidence interval for the probability of the aqueous humor being positive and/or the lenses being positive. If some results are positive, a more sophisticated approach will be used which recognizes the potential for an association in the outcome for eyes from the same individual. Since it is possible that some individuals receiving cataract surgery in both eyes will have discordant results, generalized estimating equations with a logistic link will be used to estimate the probability of testing positive given random effects for participants. This approach can be extended to accommodate tests for effects of age and gender (which are secondary outcomes).

Study CRFs capture the grade of anterior chamber cells for each eye according to the SUN criteria. Regression models will be fit with these grades as outcome variables and survivor status, age (less than 40 or greater than or equal to 40) and gender as explanatory variables. The test of the hypothesis of no difference in grade according to survivor status will be conducted by testing the null hypothesis that the regression coefficient associated with survivor status is zero. This will be conducted at the one and three month assessments. A significance level of 0.025 will be used for both tests to account for test multiplicity. These models will also allow for testing for the effects of gender and age, which is one of the secondary objectives. The secondary outcome about having 20/40 or better BCVA after surgery will be conducted using logistic regression with explanatory variables gender, age and survivor status.

To test for differences in postoperative structural changes after intraocular surgery between survivors and controls mixed effects models will be fit to data from the one month and three month exams for central subfield thickness and intraretinal fluid cysts. These models will also control for gender and age while testing for a difference due to survivor status. Linear models will be used for central subfield thickness and logistic regression models will be used for intraretinal fluid cysts. Tests of secondary outcomes will use a significance level of 0.05.

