To examine outcomes at the nine and 12 month exams, similar models will be fit but they will be extended to these later exams.

If less than 10% of participants have any cells observed in the anterior chamber, then the second primary outcome will be having cells detected (a dichotomous outcome) and the regression modeling strategy will be replaced with a logistic regression modeling approach.

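### The cell-grade model adjusts for age only as under 40 versus 40 or over, which can leave residual age confounding and weakens the planned age test

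*Combined protocol and SAP*

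**What the plan says.** Section 9.1 fits regression models to cell grade with "survivor status, age (less than 40 or greater than or equal to 40) and gender as explanatory variables". The primary test is whether the survivor coefficient is zero, at one month and at three months, each at 0.025. The same fits serve a second purpose: "These models will also allow for testing for the effects of gender and age, which is one of the secondary objectives". Secondary tests use 0.05. If fewer than 10% of participants have any cells, the outcome becomes cells present or absent and "the regression modeling strategy will be replaced with a logistic regression modeling approach".

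No reason is given for the cut at 40, and no other form of age is planned as a check. The visual acuity and optical coherence tomography models also include age, but their coding is not stated.

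Three other places bear on the point:

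- Section 9.0: "This protocol has sample sizes of convenience". Nothing describes matching on age.
- Section 3.1.1: "Participant must be 14 years of age or older", with no upper limit.
- Section 1.1: "Intraocular surgery among young individuals is also often marked by a robust inflammatory response", and then, of this and viral persistence in the lens, "Both factors may influence outcomes in Ebola-associated cataract".

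**The concern.** Survivors and controls are not randomised, so regression adjustment is the only protection against an age difference between them. Such a difference is plausible: Section 1.1 says these cataracts may follow inflammation or steroid use, or may develop naturally, and the mix of causes could differ by group. Under the planned coding a 15-year-old and a 39-year-old count as the same age. Any difference in age within a band stays in the survivor coefficient.

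If survivors are the younger group and younger eyes inflame more, an age effect could be read as a survivor effect. If survivors are older, a real survivor excess could be hidden. The documents do not say which group is younger, so the direction is unknown.

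The age test has a separate problem. Cutting age at 40 discards information within each band, and this costs power whenever the age effect is gradual, even if the two groups have identical ages.

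**Working it through.** **The plan's own figure.** Section 9.2 gives power for Fisher's exact test with 60 per group, a control rate of 0.004 and a significance level of 0.025. Exact enumeration, two-sided, gives 0.374, 0.522, 0.685, 0.810 and 0.893, against 0.38, 0.52, 0.69, 0.81 and 0.89 in Table 1. All agree to within 0.01. This calculation has no age term, so it neither supports nor contradicts the age coding.

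**Inputs.** From the documents: the age coding, the significance levels, 60 per group (Section 9.2), and the expected recruitment, "Current estimates of numbers of survivors and controls meeting eligibility criteria is lower, at about 35-45 survivors and 35 controls" (Section 3.0). Assumed, because the documents give none: age distributions, the size and shape of the age effect, and how many participants have cells after surgery.

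**1. Share of the age difference left in the survivor coefficient.** Let D = 1 if age is 40 or over. For an outcome linear in age, least squares on survivor status and D leaves

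residual = (age gap) − γ × (gap in the proportion with D = 1), where γ = pooled within-group cov(age, D) / pooled within-group var(D).

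Take normal ages with SD 14 and means 35 and 50:

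- Proportions aged 40 or over: 0.3605 and 0.7625, a gap of 0.4020.
- cov(age, D) = SD × normal density at the cut: 5.240 and 4.328, mean 4.784.
- var(D): 0.2305 and 0.1811, mean 0.2058.
- γ = 4.784 / 0.2058 = 23.24.
- Residual = 15 − 23.24 × 0.4020 = 5.66 years, and 5.66 / 15 = 38%.

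The same formula gives 37% for means 35 and 45, and 41% for 35 and 55. With SD 12 and ages restricted to 14 or over, the shares are 35%, 38% and 43% for means of 35 against 45, 50 and 55. Other shapes give 28%-42% (a step at 30), 53% (flat ages 14-60 against 20-80, linear effect) and 0% (a step exactly at 40, or two age clusters either side of 40). Age in years leaves 0% when the effect is linear.

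**2. Type I error of the survivor test, nominal 2.5%.** Setting: cell grade 0 to 4 from a proportional-odds model with no survivor effect, mean ages 35 and 50, odds ratio 1.5 to 3 per decade younger, least-squares test adjusted for gender and age, 8,000 trials per setting. The simulation standard error is √(0.025 × 0.975 / 8,000) = 0.17 percentage points.

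| Participants with cells | Cut at 40, 60/60 | Cut at 40, 40/35 |
|---|---|---|
| 10% | 1.2%-2.1% | 0.6%-1.8% |
| 20% | 2.5%-3.0% | 1.4%-2.0% |
| 40% | 3.4%-7.6% | 2.6%-4.3% |
| 60% | 4.1%-12.5% | 3.2%-7.8% |

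With age in years the range over all these settings is 1.3%-2.9% at 60/60 and 1.2%-2.5% at 40/35. Smaller gaps matter less: at 40% with cells and 60/60, the cut gives 2.6%-3.0% for 5 years and 2.9%-5.0% for 10 years. Reversing which group is younger reverses the bias, from +0.12 to −0.12 grade at odds ratio 2 and 40% with cells. For a binary outcome at 5.4% prevalence there is no inflation: the logistic Wald test rejects at 0.2%-0.6% with the cut and 0.5%-1.1% with age in years.

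**3. Power of the age test at 0.05, with no age gap.** An approximation is power = Φ(atanh(ρk)√(N − 5) − 1.96), where ρ is the age-grade correlation and k the correlation of age with its indicator (k = 1 for age in years). Assume ρ = 0.3 and ages with mean 40 and SD 15, so k = 0.797 and k² = 0.64 of the information is kept.

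- N = 120, years: 0.3095 × 10.72 − 1.96 = 1.36, power 91%. Cut: 0.2438 × 10.72 − 1.96 = 0.65, power 74%.
- N = 75: 74% for years, 53% for the cut.

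The ordinal simulation, with both groups at mean age 42 and 60/60, gives for cut against years:

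| Participants with cells | Odds ratio 1.5 | Odds ratio 2 |
|---|---|---|
| 20% | 29% vs 38% | 62% vs 78% |
| 40% | 43% vs 60% | 84% vs 95% |

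At 10% with cells and odds ratio 2 it is 40% against 52%. If the true effect is a step exactly at 40, the order reverses: 61% for the cut against 38% for years in one setting. Linear age then still holds the survivor test at 1.9%-2.2%.

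**The case against.** The strongest reply is that the plan's own rates point to rare cells, where nothing is inflated. Section 9.2 assumes 10.4% against 0.4%, and Table 1 stops at 18%. At equal group sizes the pooled rates are (10.4 + 0.4)/2 = 5.4% to (18 + 0.4)/2 = 9.2%, all below the 10% trigger for the logistic fallback. Treating these eye rates as participant rates, the fallback would apply with probability 97% falling to 57% at 60/60, and 94% falling to 54% at 40/35. The larger error rates need a 15-year gap, common cells and a strong age effect together. At the expected recruitment and 20% with cells there is no inflation. The planned term already removes 57%-65% of the age-driven difference in the normal-age linear cases, and linearity is itself an assumption.

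Most of this stands, and it limits the point to a refinement. Two parts do not remove it. First, the Section 9.2 rates come from PREVAIL III eyes and are not postoperative rates; the grade model is used only when at least 10% of participants have cells, and that is where inflation can begin. Second, the loss in the age test needs no age gap and still appears at 10% with cells. Small numbers do not justify the cut, because linear age uses the same one degree of freedom. The linearity assumption can be checked with a sensitivity analysis.

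**Conclusion.** The concern holds, conditionally. With a gradual age effect and an age gap between groups, the cut at 40 leaves roughly 35% to 43% of the age-driven difference in the survivor coefficient under normal ages with gaps of 10 to 20 years. The type I error stays at or below nominal when about 5%-10% have cells. With a 15-year gap at 60/60 it reaches 3.4%-7.6% at 40% with cells, and 12.5% in the most extreme setting examined. With no age gap there is no bias. The loss of power in the age test is the firmer part: about 9 to 17 percentage points in the simulated settings, subject only to the effect being gradual. All sizes rest on assumed ages, age effects and cell rates. This is not a fatal flaw, but the change is worth making because it costs little.

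**What to change.** In Section 9.1, replace the two-band age term with *survivor status, age in years (continuous) and gender*. In addition:

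- Use the same single age term in the logistic fallback, and state the age coding for the visual acuity and optical coherence tomography models.
- For the cell-grade model only, add a sensitivity analysis with a quadratic or three-knot restricted cubic spline in age. Events would be too few for this in the fallback.
- Keep under 40 versus 40 or over as a second sensitivity analysis and in descriptive tables.
- Report the age distribution by group.

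The cost is a change of wording for the main model, short statements for the other models and the sensitivity analyses, and one descriptive table. No new data are needed, because assigning the bands already requires each participant's age. The real downside is lower power in the age test if the true effect is a step at 40, which the retained banded analysis would show.

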# 9.2 Power Analysis

We plan to enroll up to 120 participants of which 60 will be survivors and 60 contacts, to have cataract surgery as part of this protocol. The accrual ceiling is 120. If none of 40 samples test positive for Ebola RNA then a 95% confidence interval for the probability of testing positive will be (0.0, 0.09) indicating that we can conclude this occurs in less than 9% of cases. If 60 samples are obtained, then the 95% confidence interval for the probability of testing positive will be (0.0, 0.06) indicating that we can conclude this occurs in less than 6% of cases.

To examine the power for the association between survivor status and cell grade, we assume that we are just testing for a difference in the frequency with which anterior cells are observed in the two groups using Fisher's exact test. Results from PREVAIL III indicate that 10.4% of the eyes of survivors with cataracts have anterior chamber cells while only 0.4% of the eyes of contacts have cells observed. If we suppose that there are 60 participants in each group, then we have 38% power for detecting a difference using these two estimates (using a significance level of 0.025). If the rate among survivors is higher than this due to ongoing inflammation, then the power rapidly increases. Table 1 shows the power as it depends on the proportion of eyes with anterior chamber cells among survivors.

Table 1

Proportion	0.104	0.12	0.14	0.16	0.18
Power	0.38	0.52	0.69	0.81	0.89

**Table 1:** The power for the second primary aim using a dichotomous outcome. The proportion of eyes with cells among contacts is assumed to be 0.004 (the observed rate in PREVAIL III among contacts) while this proportion in survivors varies from 0.104 (the observed rate) to higher rates.

If participants do not follow instructions to take medication or return on the advised schedule, data will be analyzed using an intent-to-treat classification.

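### Optional refinement: Holm's step-down in place of a fixed 0.025 at months 1 and 3 keeps the 5% family-wise error and never rejects less, but does not relieve the low power

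*Combined protocol and SAP*

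**What the plan says.** The second primary outcome (Sections 2.1 and 8.1) compares average anterior chamber cell grade between survivors and controls at 1 and 3 months after surgery. Section 9.1 fits regression models adjusted for age and gender and tests survivor status by "testing the null hypothesis that the regression coefficient associated with survivor status is zero". It continues: "This will be conducted at the one and three month assessments", and then "A significance level of 0.025 will be used for both tests to account for test multiplicity". No step-down rule and no ordering of the two visits is given. The other primary outcome, viral persistence, is estimated with a 95% confidence interval and not tested, so these two tests use the whole 5%.

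Section 9.2 simplifies the comparison to a "difference in the frequency with which anterior cells are observed in the two groups using Fisher's exact test". Its inputs are that "10.4% of the eyes of survivors with cataracts have anterior chamber cells while only 0.4% of the eyes of contacts have cells observed". Taking groups of 60 and the 0.025 level, the section concludes: "then we have 38% power for detecting a difference". That figure is for a single test. No power is stated for showing a difference at both visits.

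**The concern.** A fixed 0.025 at each visit gives up some power for no gain in error control. Suppose month 1 gives p = 0.01 and month 3 gives p = 0.04. The current rule declares a difference at month 1 only, while Holm declares one at both with the same 5% family-wise guarantee.

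This has some weight here for two reasons. Power is low by the plan's own account and the samples are ones of convenience (Section 9.0), so adding participants is not an easy remedy. Section 1.2 also asks whether survivors have prolonged inflammation after surgery, and a difference at both visits would speak to that more directly than a difference at one.

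**Working it through.** **1. Reproduce the plan's power.** Inputs from Section 9.2: 60 per group, contact rate 0.004, survivor rate 0.104 to 0.18, Fisher's exact test at 0.025. Sidedness is not stated. Exact enumeration of the two-sided test over Binomial(60, p) × Binomial(60, 0.004) gives:

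| Survivor rate | Table 1 | Exact power at 0.025 (a) | Exact power at 0.05 (b) |
|---|---|---|---|
| 0.104 | 0.38 | 0.374 | 0.530 |
| 0.12 | 0.52 | 0.522 | 0.669 |
| 0.14 | 0.69 | 0.685 | 0.802 |
| 0.16 | 0.81 | 0.810 | 0.891 |
| 0.18 | 0.89 | 0.893 | 0.943 |

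Table 1 reproduces. A one-sided test at 0.025 would give 0.530 at the first rate, so two-sided is the right reading.

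**2. Error control under Holm.** Holm tests the smaller p-value at 0.025 and, if it is significant, the other at 0.05.

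- Both nulls true: an error needs at least one p-value at or below 0.025, so its probability is at most 0.025 + 0.025 = 0.05.
- One null true: an error needs that p-value at or below 0.05, so its probability is at most 0.05.

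Neither step uses the correlation between visits. Simulated normal tests with both nulls true gave 0.049, 0.046 and 0.036 at correlations 0, 0.5 and 0.9.

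**3. Gain with independent visits.** Assume the same rates at both visits. At 60 per group and rate 0.104:

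- Both visits, fixed 0.025: a² = 0.374² = 0.140.
- Both visits, Holm: a² + 2a(b − a) = 0.140 + 2 × 0.374 × 0.156 = 0.257 (0.256 from unrounded values).
- Per visit, Holm: a + a(b − a) = 0.374 + 0.374 × 0.156 = 0.432.
- At least one visit, either rule: 1 − (1 − 0.374)² = 0.608.

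**4. Gain with correlated visits.** Simulation with exact Fisher p-values, equal rates at both visits and latent within-participant correlation 0.5. Control rate 0.004; groups are survivors/controls; each cell shows fixed 0.025 → Holm.

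| Groups | Survivor rate | Per visit | Both visits |
|---|---|---|---|
| 60/60 | 0.104 | 0.37 → 0.43 | 0.17 → 0.29 |
| 60/60 | 0.14 | 0.69 → 0.76 | 0.51 → 0.65 |
| 40/35 | 0.104 | 0.10 → 0.12 | 0.02 → 0.05 |
| 45/35 | 0.104 | 0.16 → 0.18 | 0.04 → 0.09 |
| 35/35 | 0.104 | 0.13 → 0.13 | 0.03 → 0.03 |
| 40/35 | 0.18 | 0.56 → 0.64 | 0.36 → 0.51 |
| 35/35 | 0.18 | not computed | 0.35 → 0.37 |

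The smaller groups are those that Section 3.0 expects: about 35 to 45 survivors and 35 controls. At 35/35 almost nothing is gained because Fisher's test is discrete: exact single-test power at rate 0.104 is 0.132 at 0.025 and 0.134 at 0.05.

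**5. Sensitivity at 60/60, rate 0.104.** Both-visit power is 0.219 → 0.338 at correlation 0.8, 0.269 → 0.379 at 0.95, and 0.374 → 0.374 at 1.0, where the visits give identical results and nothing is gained. If the survivor rate falls to 0.05 at month 3 (an assumption), both-visit power goes from 0.015 to 0.039.

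**The case against.** The strongest reply is that nothing in the plan is wrong. Bonferroni is valid, it is pre-specified, and the stated power matches the stated level. That stands in full.

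A reader might infer that Holm eases the 38% power. It does not. Its first step is the same test at 0.025, so a trial that shows nothing under the current rule shows nothing under Holm. At 60/60, rate 0.104 and correlation 0.5, the chance of at least one significant visit is about 0.57 under both rules.

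A reader might also take both-visit power as the trial's measure of success. Sections 2.1, 8.1 and 9.1 call for a comparison at each visit and do not require significance at both. Section 1.2 gives the both-visit reading some support, but no success criterion. On the per-visit measure, the one the plan does power, the gain is about 6 points at 60/60 and 0 to 2 points at the expected enrolment with rate 0.104.

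Finally, two tests at equal levels have simple matching 97.5% intervals. In a natural history study where estimates matter, preferring that match is defensible. This is a real cost of Holm, though a small one.

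**Conclusion.** The point holds as a cheap, optional improvement and not as an error. Holm gives the same family-wise guarantee without any added assumption and never rejects less.

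Its benefit depends on conditions that the documents do not settle. At 60/60 with correlation 0.5, both-visit power rises by 12 points at rate 0.104 (0.17 to 0.29) and by 14 points at rate 0.14 (0.51 to 0.65). At the expected enrolment with rate 0.104 it rises by 0 to 5 points and stays below 0.10. Holm therefore does not cure the low power.

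The power figures rest on equal rates at both visits and on the assumed correlation, neither of which is in the documents. They also rest on Section 9.2's own Fisher simplification of the adjusted regression. The error control and the never-rejects-less property need none of these assumptions. They carry over to any valid pair of p-values, including those from the logistic fallback in Section 9.1.

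**What to change.** Replace the significance-level sentence in Section 9.1 with: *The smaller of the two p-values is tested at 0.025; if significant, the other is tested at 0.05 (Holm).* Make the change before the outcome data are examined.

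It needs no new data, visits or models, and the power figures in Section 9.2 can stay as the power of a single test at 0.025. If 97.5% simultaneous intervals are reported, add a line saying that they correspond to the fixed 0.025 tests. An interval may then include no difference at a visit that Holm declares significant.

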## Post-operative visit #1: 1 day after surgery

All participants who have undergone surgery will return after one day for standard postoperative assessment, during which they will undergo vision assessment and slit-lamp biomicroscopy. The degree of intraocular inflammation will be recorded.

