## 8.0 OUTCOME MEASURES

# 8.1 Primary Outcome

The primary outcomes are: 1) the proportion of EVD survivors with evidence of persistence of Ebola virus in ocular tissue and 2) comparison of the amount of intraocular inflammation, as measured by average grade of anterior chamber cell by SUN criteria, between EVD survivors and controls at 1 month and 3 months following cataract surgery.

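### At the plan's own cell rates the second primary outcome will probably switch from SUN grade to presence of cells, under a rule that names no visit and a logistic test that fails when controls have no cells

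*Combined protocol and SAP*

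**What the plan says.** The Précis and sections 2.1 and 8.1 define the second primary outcome as intraocular inflammation "as measured by average grade of anterior chamber cell by SUN criteria, between EVD survivors and controls at 1 month and 3 months" after surgery. For this outcome section 9.1 states: "Regression models will be fit with these grades as outcome variables". Survivor status, age in two bands and gender are the explanatory variables, and the survivor coefficient is tested against zero at each visit: "A significance level of 0.025 will be used for both tests to account for test multiplicity". The type of regression is not named for the grade, although the same section names linear models for central subfield thickness.

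Section 9.1 then ends with a switch: "If less than 10% of participants have any cells observed in the anterior chamber, then the second primary outcome will be having cells detected", in which case "the regression modeling strategy will be replaced with a logistic regression modeling approach". It does not say at which visit the 10% is counted, or whether the two visits switch together.

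Section 9.2 gives power only for the yes/no version, by Fisher's exact test with 60 per group: 0.38 at 10.4% against 0.4%, rising to 0.89 at 18% (Table 1). Section 3.0 expects fewer participants, about 35 to 45 survivors and 35 controls.

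**The concern.** The outcome named in three places may not be the one analysed. The plan gives no power for it, and its own planning rates lie well under the trigger.

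The trigger can also be applied in more than one way. Counted separately at Months 1 and 3, it can leave the two co-primary tests on different outcomes. Counted over all visits, it could take in the Day 1 examination, where section 4.3 says "The degree of intraocular inflammation will be recorded". An analyst could choose between these readings after seeing the data.

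Finally, the likely branch is a covariate-adjusted logistic regression in which one group is expected to have almost no events. Table 1 describes a different test, so a reader of section 9.2 would overestimate what the planned analysis can detect.

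**Working it through.** **Inputs.** Survivor rates 0.104, 0.12, 0.14, 0.16 and 0.18, control rate 0.004, 60 per group, level 0.025 (sections 9.1 and 9.2). Expected sizes of 35 to 45 survivors and 35 controls (section 3.0).

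**1. The plan's own figure.** Enumerating two binomials (60/60) with a two-sided Fisher's exact test at 0.025 gives 0.374, 0.522, 0.685, 0.81 and 0.893. Table 1 has 0.38, 0.52, 0.69, 0.81 and 0.89, so it is reproduced. The same calculation at 40/35 and 0.104 gives 0.10.

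**2. Probability of the switch.** The expected pooled rate is (n1·p1 + n2·0.004)/(n1 + n2). At 60/60 it runs from (0.104 + 0.004)/2 = 5.4% to (0.18 + 0.004)/2 = 9.2%. The switch needs 11 or fewer of 120 participants with cells, or 7 or fewer of 75 or of 80. Convolving the two binomials gives:

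| Survivor rate | 0.104 | 0.12 | 0.14 | 0.16 | 0.18 |
|---|---|---|---|---|---|
| 60/60 | 0.974 | 0.937 | 0.852 | 0.727 | 0.574 |
| 40/35 | 0.939 | 0.886 | 0.792 | 0.673 | 0.544 |

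At 0.104 it is 0.90 for 45/35 and 0.92 for 35/35. At 0.18 and 45/35 it is 0.40. If post-operative rates were 20% and 5% (an assumption; pooled 12.5%), it is 0.16 at 60/60.

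**3. Different outcomes at the two visits.** If the rule is applied per visit and the two counts are independent (an assumption), the chance that exactly one visit switches is 2s(1 − s), with s the switch probability. At 60/60: 2 × 0.974 × 0.026 = 0.05 at 0.104; 2 × 0.727 × 0.273 = 0.40 at 0.16; 2 × 0.574 × 0.426 = 0.49 at 0.18.

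**4. The yes/no branch.** The chance that no control has cells is 0.996^60 = 0.79, or 0.996^35 = 0.87. The data are then separated and the survivor coefficient has no finite estimate. In simulations with two binary covariates at 0.104 against 0.004, the logistic Wald test had power of about 0.02 at 60/60 and 0.002 or less at 40/35. The likelihood-ratio test had 0.77 to 0.78 at 60/60, but its type I error at a common 5.4% rate was about 0.04 against 0.025, so that power is not usable. A rank test with a permutation p-value, unadjusted, had about 0.40 to 0.43 at 60/60 and 0.12 to 0.14 at 40/35.

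**5. The grade branch.** The documents give no grade distribution, so every mix here is assumed. The test called linear is least squares on the grade scored 0, 0.5, 1, 2, 3, 4. Power at 60/60 and level 0.025:

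| Scenario | Linear | Fisher | Rank |
|---|---|---|---|
| 30% v 5%, positives 65/25/7/2/1% at 0.5/1/2/3/4 | 0.81 | 0.92 | 0.94 |
| 30% v 5%, positives 80% at 0.5 and 20% at 1 | 0.91 | 0.91 | 0.94 |
| 30% v 5%, all positives at 0.5 | 0.94 | 0.91 | 0.94 |
| 30% v 10%, controls all at 0.5, survivors heavier | 0.98 | 0.81 (rank) is the nearer rival; Fisher 0.65 | 0.81 |

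**The case against.** The switch is written down in advance, has a numerical threshold, and reads as a count over both groups together, so it does not look at the comparison. A reader might infer that the switch inflates the type I error. The calculations do not support that: in null simulations at common rates from 0.4% to 20%, the whole procedure (linear model, or Wald logistic after a switch) rejected at most 2.4% of the time. Section 9.2 is also open about powering the yes/no version.

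The planning rates come from PREVAIL III eyes, not from eyes one to three months after surgery, and section 9.2 itself allows for higher rates from ongoing inflammation. This stands. It makes the switch probability conditional, but does not settle which outcome will be analysed.

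The all-visits reading that brings in Day 1 is strained, because the outcome is defined at Months 1 and 3 only. This also stands, but the choice between one count and two separate counts at those visits remains open.

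A reader might also infer that the grade branch is linear and is the weaker test. The documents never call the grade model linear; the words average grade only lean that way. If it is linear, the ranking turns on the assumed grades. It loses to a rank test when the groups differ mainly in how often cells occur and some grades are high, is similar when grades are mild, and is clearly stronger when survivors' cells are also heavier. Section 1.1 gives severe post-operative inflammation as a reason for monitoring, so that last case matters.

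**Conclusion.** The point holds in a limited form. At the plan's own rates the named outcome gives way to presence of cells with probability 0.97 (60/60) or 0.90 to 0.94 (expected sizes). The claim that average grade is unlikely to be analysed rests on those rates and fails if post-operative cells are much commoner. Two defects do not depend on that probability: the trigger has no visit, and the type of grade model is not stated.

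The more damaging defect is in the likely branch. With no control events 79% to 87% of the time, the planned coefficient test has almost no power if it is a Wald test, and is anti-conservative if it is a likelihood-ratio test. Section 9.1 does not say which is meant. Table 1 describes neither. The documents do not support a general claim that a linear grade analysis is the weaker test, and none is made here.

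**What to change.** In section 9.1 delete the 10% switch and state, in substance: the SUN grade of the operated eye at each of Months 1 and 3 will be analysed by one proportional-odds model with survivor status, age band and gender; the survivor term will be tested at 0.025 per visit by a permutation p-value, not a Wald or likelihood-ratio p-value; the proportion with any cells will be reported by group. The permuted quantity should be a score statistic, which stays finite when controls have no cells. With only two grades observed the model reduces to logistic regression, so no switch is needed. Match the wording of the Précis and sections 2.1 and 8.1, and give power for this test in section 9.2 at the expected enrolment.

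If the sponsor keeps the rule, apply it once, to operated eyes at Months 1 and 3 together, so that both visits use the same outcome; name the grade model; and use an exact or penalised method for the yes/no version.

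The cost is wording. The method has less power than a comparison of mean grades when survivors' cells are also of higher grade, and it does not cure the low power at 40/35.
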